9.6 Genetics

At screening and end of treatment, peripheral blood sampling for pharmacogenomic analysis is mandatory and participant must consent to the collection of these samples. Samples should be collected when bone marrow is collected at protocol specified time points and must be collected on the same day as the bone marrow aspirate procedure.

Refer to the Laboratory Manual for sample collection, handling, and processing instructions.

Other correlative assessments may include, but are not limited to, AML gene mutation sequencing and DNA methylation. Results from these studies will be evaluated in association with parameters of clinical benefit to determine whether biomarkers of response or non-response to treatment may be identified.

9.7 Biomarkers

Collection of samples for other biomarker research is also part of this study. The following samples for biomarker research are required and will be collected from all participants in this study as specified in Table 9.7-1. The date and time of collection will be recorded in the source documents and eCRFs.

At baseline and post treatment, bone marrow aspirate (BMA) samples will be collected for assessing disease and response (ie, cytomorphology, cytogenetics, minimal residual disease). If adequate BMA is not obtainable, then a bone marrow biopsy should be completed.

Refer to the Laboratory Manual for sample collection, handling, and processing instructions.

Table 9.7-1: Biomarker Sampling Schedule (All Participants)

Study Day of Sample Collection (1 Cycle = 4 Weeks) ^a	Pharmacogenomic Blood Sample	Bone Marrow Aspirate (MRD) ^b	Biomarker Blood Assessment (PD) ^c	Biomarker Bone Marrow Assessment (NGS) ^d
Screening	X	X	X	X ^d
Cycle 1 Day 1			X	
Cycle 3 Day 1		X	X	
Cycle 6 Day 1		X		
Cycle 9 Day 1		X		
Cycle 12 Day 1		X		
Cycle 15 Day 1		X		
Cycle 18 Day 1		X		
Cycle 21 Day 1		X		
Cycle 24 Day 1		X		
Cycle 30 Day 1		X		
Cycle 36 Day 1		X		
EOT	X	X		

Abbreviations: DNA, deoxyribonucleic acid; EOT, end of treatment; IgG, immunoglobulin G; IgM, immunoglobulin M; MRD, minimal residual disease; NGS, next generation sequencing; PD, pharmacodynamic.

^a All sample collection for biomarker assessments will be done predose at the selected time points.

^b Suggested MRD time points to parallel clinical assessment.

^c Pharmacodynamics blood samples (for DNA methylation analyses) will be collected predose at the time points indicated.

^d Targeted sequencing of AML-specific genes (gene panel) using NGS will be conducted on screening samples.

9.8 Additional Research

This protocol will include residual sample storage for additional research. Additional and optional research as described below may be performed using leftover samples originally collected for another test required in this study or using samples collected specifically for biomarker testing. The research may involve genetic tests using DNA or RNA and may lead to the development of new diagnostic tests.

- Additional research related to the study intervention and/or disease may be performed. The results of this additional research could help to improve the diagnosis and/or the treatment of this disease in the future.
- Optional research not related to the study intervention or the participant's disease may be performed. The participant's decision to participate in this optional research will not impact his/her ability to participate in the main study.

For All sites:

Additional research is required for all study participants, except where prohibited by IRB/ethics committees, prohibited by local laws or regulations, or academic/institutional requirements. Where one or more of these exceptions occurs, participation in the additional research should be encouraged but will not be a condition of overall study participation.

- If the IRB/ethics committees and site agree to the mandatory additional research retention and/or collection, then the study participant must agree to the mandatory additional research as a requirement for inclusion in the study.
- If optional participation is permitted and approved, then the study participants may opt out of the additional research retention and/or collection.

Additional research is intended to expand the R&D capability at Bristol-Myers Squibb, and will support as yet undefined research aims that will advance our understanding of disease and options for treatment. This may also include genetic/genomic exploration aimed at exploring disease pathways, progression and response to treatment etc.

Sample Collection and Storage

Residual blood and bone marrow samplings from biomarker collections (see [Table 9.7-1](#)) will also be retained for additional research purposes.

Samples kept for future research will be stored at the BMS Biorepository in [REDACTED], or an independent, BMS-approved storage vendor.

The manager of these samples will ensure they are properly used throughout their usable life and will destroy the samples at the end of the scheduled storage period, no longer than fifteen (15) years after the end of the study or the maximum allowed by applicable law.

Transfers of samples by research sponsor to third parties will be participant to the recipient's agreement to establish similar storage procedures.

Samples will be stored in a coded fashion, and no researcher will have access to the key. The key is securely held by the Investigator at the clinical site, so there is no direct ability for a researcher to connect a sample to a specific individual.

Further details of sample collection and processing will be provided to the site in the procedure manual.

9.9 Health Economics OR Medical Resource Utilization and Health Economics

Health economics/medical resource utilization and health economics parameters will not be evaluated in this study.

10 STATISTICAL CONSIDERATIONS

10.1 Statistical Hypotheses

The primary endpoint is RFS. Based on the median RFS in the CC-486 and placebo groups of Study CC-486-AML-001, the expected median RFS was set at 4.8 months for placebo, and the expected median RFS was set at 9.5 months for CC-486.

As the primary efficacy analysis, a Cox proportional hazards model will be used to estimate the corresponding hazard ratio and 95% CI for CC-486 relative to placebo. RFS curves will be estimated using Kaplan-Meier (KM) methods. The primary objective of this study is to estimate the efficacy of CC-486 as maintenance therapy by using RFS. The study does not plan to conduct any formal statistical hypothetical testing. For participants who do not have an RFS event, their RFS time will be censored at the last contact date (or "last known RFS date"). RFS will be censored at the date of randomization for participants who were randomized but had no response assessment.

Analysis of the primary endpoint will be conducted when the last subject completes 12 months follow-up. However, it may need to be reconsidered depending on the occurrence status of the event.

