Biomarker Blood and Bone Marrow Sampling (from the same sample taken for central review; additional consent required)	X		Refer to biomarker collection table in Section 9.7 for timing of collections. Blood and bone marrow samples for biomarker assessment are mandatory and participant must consent to the collection of these samples. Samples should be collected when bone marrow is collected at protocol specified time points and when bone marrow is collected to confirm a response (CR or CRi) or relapse.
Pharmacogenomic Blood Sampling	X		Peripheral blood sampling for pharmacogenomic analysis is mandatory and participant must consent to the collection of these samples. Samples should be collected when bone marrow is collected at protocol specified time points and must be collected on the same day as the bone marrow aspirate procedure.

Table 2-3: End-of-treatment and Follow-up Procedural Outline (CA055005)

Procedure	End of Treatment /Early Termination	Follow-up	Notes
Efficacy Assessments			
Bone Marrow Aspirate	X		If disease relapse features are observed following a bone marrow aspirate, it is recommended that a repeat bone marrow aspirate be performed at least 3 to 4 weeks later to confirm disease relapse unless the blast count was > 50% in the marrow or peripheral blood.
Bone Marrow Biopsy	X		Bone marrow biopsy may be needed to assess bone marrow status if an adequate bone marrow aspirate cannot be attained.
Cytogenetic Testing	X		Bone marrow aspirate sample tube for cytogenetic testing/chromosome analysis to be obtained for evaluation by central laboratory to obtain karyotype.
Peripheral Blood Smear	X		Whenever bone marrow aspirate (or biopsy) slides are sent to the central reviewer, a peripheral blood smear slide should also be submitted.
IWG Response Assessment	X		Participants should be assessed for CR/CRI status maintenance, relapse after CR/CRI, or disease relapse.
Follow-up AML Relapse		X	All discontinued participants, regardless of reason for discontinuation, should be followed for AML relapse every 4 weeks (\pm 3 days) for the first year and then every 12 weeks (\pm 14 days) until death, loss to follow-up, withdrawal of consent from further follow-up, or end of study. Documentation such as laboratory or pathology reports, bone marrow reports, and/or peripheral blood reports supporting the AML relapse should be requested and collected.

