4 OBJECTIVES AND ENDPOINTS

Table 4-1: Objectives and Endpoints

Objectives	Endpoints	Estimands
Primary Objective	Primary Endpoint	Primary Estimand

• To evaluate the efficacy of CC-486 as maintenance therapy by using RFS in Japanese participants \geq 55 years with AML who have achieved first CR or CRI after induction with intensive chemotherapy with or without consolidation chemotherapy.	
• RFS	
• Population: All randomized Japanese participants \geq 55 years with AML, who have achieved first CR or CRI after induction with intensive chemotherapy with or without consolidation chemotherapy.• Treatment: CC-486 +/- BSC vs placebo +/- BSC as randomized• Intercurrent events: Participants without documented relapse at the time of study closure and participants who are withdrawn for any reason or start subsequent therapy will be censored.• Summary statistics: Kaplan-Meier curves, and hazard ratios from Cox

Table 4-1: Objectives and Endpoints

Objectives	Endpoints	Estimands

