9.1 Efficacy Assessments

9.1.1 Efficacy Assessment for the Study

International Working Group Response

International Working Group (IWG) response assessment will be assessed at Cycles 3, 6, 9, 12, 15, 18, 21, 24, 30, 36, and the Treatment Discontinuation Visit. After Cycle 36, IWG response assessment will be performed if clinically indicated at the discretion of the Investigator. Participants should be assessed for CR/CRI status maintenance or disease relapse.

Bone Marrow Aspirate, Biopsy, and Peripheral Blood Smear

Bone marrow aspirate (or biopsy if adequate aspirate is not attainable) samples during the Double-blind Treatment Phase should be collected at Screening, on Day 1 (\pm 7 days) of Cycles 3, 6, 9, 12, 15, 18, 21, 24, 30, 36, and the Treatment Discontinuation Visit. After Cycle 36, bone marrow aspirate collection and evaluation will occur if clinically indicated at the discretion of the Investigator.

Additional bone marrow samples should be collected as clinically indicated. A bone marrow biopsy must be collected if adequate aspirate is not attainable. Whenever a bone marrow sample is collected, a peripheral blood smear is to be prepared.

Instructions for submission of bone marrow samples are provided in Study Reference Manual and/or Study Central Laboratory Manual.

Cytogenetics

Bone marrow cytogenetic testing is to be completed whenever a bone marrow aspirate (or biopsy if adequate aspirate is not attainable; note that specific handling of the biopsy is required if it is to be used for cytogenetics testing [refer to the Laboratory Manual for sample collection, handling, and processing instructions]).

Follow-up AML Therapies

All discontinued participants, regardless of reason for discontinuation, should be followed for subsequent AML therapies every month for the first year and every 3 months thereafter until death, loss to follow-up, withdrawal of consent from further follow-up, or study closure. Subsequent AML therapy follow-up can be performed via the telephone.

Survival Follow-up

All discontinued participants, regardless of reason for discontinuation, should be followed for survival every month for the first year and every 3 months thereafter until death, loss to follow-up, withdrawal of consent from further follow-up, or study closure. The survival follow-up can be performed via telephone.

9.1.2 *Health-related Quality of Life*

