10.4.1 General Considerations

The primary and secondary estimands are described in [Table 4-1](#).

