10.4.2 Primary Endpoint(s)

The primary efficacy endpoint of RFS is defined as the time from randomization to the date of documented relapse after CR or CRi per central review, or death from any cause, whichever occurs first. Participants who are still alive without documented relapse after CR or CRi, or who were lost to follow-up without documented relapse, will be censored at the date of their last response assessment. Relapse after CR or CRi is defined according the IWG AML response criteria.

The primary efficacy analysis will be conducted for the ITT Population and will compare the RFS distributions between the two treatment groups. A Cox proportional hazards model will be used to estimate the corresponding hazard ratio and 95% CI for CC-486 relative to placebo. The RFS curves will be estimated for the primary efficacy endpoint, time to the date of documented relapse after CR or CRi or death from any cause, whichever occurs first, using Kaplan-Meier (KM) methods. Kaplan-Meier estimates for median RFS as well as the 25th and 75th percentiles and associated two-sided 95% CIs will be summarized for each treatment group. Plots of the KM survival curves will be presented for the two treatment groups.

Additionally, KM methods will be used to estimate the 1-year and 2-year RFS probabilities for time to death from any cause. Estimates of the 1-year (365 days) and 2-year (730 days) survival probabilities and corresponding 95% confidence intervals will be presented by treatment group.

Additional sensitivity analyses, based on the mITT Population and the ITT Population, will be performed using modified RFS definitions. For these analyses of RFS, participants lost to follow-up without documented relapse will be 1) considered as having an event and 2) considered as having an event if they were randomized to the CC-486 treatment group and censored if they were randomized to the placebo treatment group. The event/censoring time will be the date of the last response assessment.

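### Primary RFS has two censoring dates (10.1 and 10.4.2), and Table 4-1 adds an undated subsequent-therapy rule that 10.4.2 does not carry

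*Combined protocol and SAP*

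**What the plan says.** Three current parts of the protocol define censoring for RFS.

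- **Section 10.1:** "For participants who do not have an RFS event, their RFS time will be censored at the last contact date". A parenthesis offers a last known RFS date as an alternative and does not define it. The next sentence adds: "RFS will be censored at the date of randomization for participants who were randomized but had no response assessment".
- **Section 10.4.2:** participants alive without relapse, and those "who were lost to follow-up without documented relapse, will be censored at the date of their last response assessment". The sensitivity analyses use the same date.
- **Table 4-1, primary estimand:** "participants who are withdrawn for any reason or start subsequent therapy will be censored". No censoring date is given. Section 10.4.1 brings the table in by cross-reference ("The primary and secondary estimands are described in"), but neither 10.1 nor 10.4.2 mentions subsequent therapy.

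On assessment, 9.1.1 says that IWG "response assessment will be assessed at Cycles 3, 6, 9, 12, 15, 18, 21, 24, 30, 36, and the Treatment Discontinuation Visit". After treatment, Table 2-3 says that discontinued participants "should be followed for AML relapse every 4 weeks" for the first year and every 12 weeks thereafter. That is a separate row from IWG response assessment. Survival follow-up may be by telephone. The sensitivity analyses in 10.4.2 vary only loss to follow-up, starting with "participants lost to follow-up without documented relapse will be 1) considered as having an event".

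**The concern.** No hypothesis test is planned, so the RFS hazard ratio and the Kaplan-Meier curves are the primary result, to be set beside those of CC-486-AML-001. As written, the protocol supports more than one hazard ratio from the same data.

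Last contact is the natural rule for OS, and 10.4.3 uses it there. For RFS it can count time without a response assessment as relapse-free, for example when the last contact was a telephone call.

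The subsequent-therapy conflict is separate, because it changes which outcomes are events. Section 8.1 foresees stops without relapse (participant's request, adverse event, becoming eligible for transplant), and 8.1.1 keeps such participants in follow-up.

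**Working it through.** **1. The plan's own figure.** Section 10.2 gives an 87% probability that the estimated hazard ratio is below 1. With the 10.1 medians, HR = 4.8/9.5 = 0.505 and |ln HR| = 0.683. For d events at 2:1 allocation, P = Φ(√(d × 2/9) × 0.683). This gives 86.8% for d = 12 and 87.7% for d = 13, so the figure reproduces. The censoring conflict does not show it to be wrong.

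**2. One participant.** Suppose someone stops in remission at Cycle 6 Day 1 (5 × 28 = day 140) and is event-free at 12 months.

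- 10.1, last contact: 365 days.
- 10.4.2, if off-treatment relapse checks are not response assessments: 140 days.
- 10.4.2, if they are: 140 + 8 × 28 = 364 days.

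The date conflict therefore turns on whether Table 2-3 relapse follow-up counts as a response assessment. The plan does not say.

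**3. One arm (invented data).** Take 10 participants with events at 2, 5, 8 and 11 months. Three are last assessed at 4.6 months (day 140) but contacted to month 12, and three are assessed to month 12. The 12-month Kaplan-Meier RFS is:

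- last contact: 9/10 × 8/9 × 7/8 × 6/7 = 60%
- last assessment: 9/10 × 5/6 × 4/5 × 3/4 = 45%

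**4. Simulated 10 versus 5 trials** (4,000 per scenario, Cox model with Efron ties).

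- *From the documents:* medians 9.5 and 4.8 months, visit and IWG schedules, Table 2-3 intervals, analysis 12 months after the last entry, median survival after relapse of 3–12 months.
- *Assumed:* exponential RFS, 24-month uniform accrual, stopping in remission at 0.01–0.03 per month (10–26% of CC-486, 6–17% of placebo).

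Date conflict, 10.1 against 10.4.2:

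| Table 2-3 follow-up counts for | HR differs >10% | HR differs >20% | Opposite sides of 1 |
|---|---|---|---|
| relapse and censoring | 0–4% | at most 1.4% | at most 1% |
| relapse only | 14–41% | 6–21% | 2–4% |
| neither | 19–70% | 9–49% | 3–10% |

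With no stopping, the >10% share is at most 2%. With 12-month accrual, the largest >10% shares in the three rows are 7%, 49% and 74%.

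Large-sample hazard ratios, 10.1 versus 10.4.2:

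- Counts for both: 0.51 versus 0.51.
- Counts for neither: 0.52 versus 0.53 (equal stopping, 0.02 per month), 0.48 versus 0.52 (CC-486 0.03, placebo 0.01), 0.57 versus 0.53 (CC-486 0.01, placebo 0.03).

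Subsequent-therapy conflict, 10.4.2 against Table 4-1, assuming half or all stoppers start new therapy: the hazard ratio differs by more than 20% in 10–49% of trials (counts for both), 8–42% (relapse only) or 4–36% (neither). It crosses 1 in 1–9%. With follow-up counted for both and stopping unrelated to prognosis, the large-sample value is 0.50–0.51 under either rule.

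**5. Against the trial's precision.** With 24-month accrual about 8 CC-486 and 4.8 placebo events are expected. SE(log HR) = √(1/8 + 1/4.8) = 0.58. The ratio of the 95% limits is exp(2 × 1.96 × 0.58), about 9.6. A 20% change is ln(1.2)/0.58, about 0.3 SE.

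**The case against.** The strongest case is that the intent can be inferred. The parenthesis in 10.1 may mean the last date known to be relapse-free, and the next sentence depends on response assessment. Section 10.4.2 is the operative endpoint section and repeats its date. Table 4-1 is the proper place for intercurrent events, and a SAP is due before database lock. Much of this stands: the intent is probably assessment-based. But 10.1 then offers two different dates in one sentence, and the SAP cannot follow all three texts at once. Nor does silence in 10.4.2 settle subsequent therapy, because its event definition takes in relapses and deaths without that exception.

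Some stronger readings are tempting, and the documents do not support them.

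- *The 70% figure is the size of the problem.* It needs the least natural reading, which ignores relapses found off treatment although Table 2-3 requires them to be sought and documented. It also rests on assumed stopping and accrual rates. Section 6.2 excludes transplant candidates at screening, so few participants may be affected.
- *The primary result is biased.* The large-sample differences in the date conflict go either way or vanish. The subsequent-therapy rules agree in large samples when follow-up counts for both and stopping is unrelated to prognosis.
- *Off-treatment checks can simply be declared response assessments.* A primary-endpoint relapse is per central review. Section 5.1 uses that review for CR/CRi status at screening and during treatment. The Table 2-3 follow-up column schedules no marrow, smear or IWG assessment and does not say how a negative check is recorded.

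**Conclusion.** The inconsistency is real and should be removed before database lock. Two censoring dates stand for the same participants, and the estimand has an undated subsequent-therapy rule that the primary analysis section does not carry and no sensitivity analysis examines.

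The size is uncertain because the documents give no rate of stopping in remission. Under the assumed rates, the date conflict runs from negligible, if Table 2-3 follow-up counts as assessment, to a change of more than 10% in a substantial share of trials of this size. The subsequent-therapy conflict remains under every reading of Table 2-3. Both are small against a CI spanning about tenfold, and neither has a fixed direction. This is a specification to harmonise while treatment codes are still restricted. It is not evidence of bias.

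**What to change.** (a) In 10.1, replace the last contact date and its parenthetical alternative with the date of the last response assessment without relapse, as in 10.4.2. Keep last contact for OS only.

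(b) State the same subsequent-therapy rule in Table 4-1, 10.1 and 10.4.2. If the Table 4-1 rule is kept, censor at the last response assessment on or before the start of subsequent therapy, and run the analysis that ignores subsequent therapy as one sensitivity analysis.

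(c) Settle in the SAP whether off-treatment relapse follow-up counts as a response assessment, consistently with the central-review event definition.

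Cost of (a) and (b): wording changes plus one sensitivity run. For (c), if off-treatment checks are to count, the sponsor should check whether central review and the recording of negative checks need to be extended. The current text does not show that they cover this.

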8.3 Lost to Follow-up

The following actions must be taken if a participant fails to return to the clinic for a required study visit:

- All reasonable efforts must be made to locate participants to determine and report their ongoing status. This includes follow-up with persons authorized by the participant.
- Lost to follow-up is defined by the inability to reach the participant after a minimum of **three (3)** documented phone calls, faxes, or emails, as well as lack of response by participant to one (1) registered mail letter. All attempts should be documented in the participant's medical records.
- If it is determined that the participant has died, the site will use permissible local methods to obtain date and cause of death.
- If the investigator's use of third-party representative to assist in the follow-up portion of the study has been included in the participant's informed consent, then the investigator may use a Sponsor-retained third-party representative to assist site staff with obtaining the participant's contact information or other public vital status data necessary to complete the follow-up portion of the study.
- The site staff and representative will consult publicly available sources, such as public health registries and databases, in order to obtain updated contact information.
- If, after all attempts, the participant remains lost to follow-up, then the last known alive date as determined by the investigator should be reported and documented in the participant's medical records.

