10.4.3 Secondary Endpoint(s)

Overall Survival

The secondary efficacy endpoint of OS is defined as the time from randomization to death from any cause and will be calculated using the randomization date and date of death, or date of last follow-up for censored participants. All participants will be followed until dropout, death, or study termination. Participants who dropout or are alive at study termination will have their OS times censored at the time of last contact, as appropriate. OS analysis will be conducted for the ITT population.

Safety

All safety analyses will be performed on the Safety Population. Adverse events will be coded using the Medical Dictionary for Regulatory Activities (MedDRA). Adverse event listings will include the verbatim term and the MedDRA preferred term. Treatment-emergent adverse events (TEAEs) will be summarized by worst severity grade, system organ class, and preferred term. Treatment-emergent AEs leading to death or to discontinuation from treatment, AEs classified as NCI-CTCAE (Version 5.0) Grade 3 or Grade 4, AEs related to IP, and SAEs will be summarized separately. Time to discontinuation from the study due to AE will be summarized using KM methods. Listings of all deaths and all SAEs, regardless of when they occurred, will also be generated.

Pharmacokinetics

The sparse concentration-time data collected in this study may be combined with a larger dataset to help further develop and validate the population pharmacokinetic model for azacitidine and to aid in the identification of covariates that influence azacitidine pharmacokinetic and/or pharmacodynamic measures and efficacy and safety endpoints. PK population will be used for PK analysis. Noncompartmental analysis will be performed using intensive sampling data.

Health-related Quality of Life

PRO endpoints include FACIT-Fatigue and the EQ-5D-5L, and analyses will include the Health-related Quality of Life population. Summary statistics (N, mean with SD and 95% CI, median, first and third quartiles, minimum, maximum) for PRO measures at each assessment point will be provided for each treatment arm. The mean change from baseline will also be reported at each post-baseline assessment point. Additionally, for the EQ-5D-5L, the proportion of participants endorsing each response option will be calculated at each time point.

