APPENDIX 6 INTERNATIONAL WORKING GROUP AML RESPONSE CRITERIA

Hematologic Response According to IWG Criteria for AML	
Category	Definition
Morphologic Complete Remission (CR)	The following conditions should be met: 
• ANC > 1,000/μL;• Platelet count \geq 100,000/μL;• The bone marrow should contain less than 5% blast cells;• Auer rods should not be detectable;• No evidence of extramedullary disease;• Independent of transfusions.
Morphologic Complete Remission with Incomplete Blood Count Recovery (CRi)	Defined as a morphologic complete remission but the ANC count may be < 1,000/ μ L or the platelet count may be < 100,000/ μ L.
Cytogenetic Complete Remission (CRc)	Defined as morphologic complete remission with a reversion to a normal karyotype.
Relapse Free Survival	Defined for patients who achieve CR/CRi, and is measured from the date of attaining leukemia free state until the date of AML relapse or death from any cause, whichever occurs first.
Disease Relapse	Relapse after CR/CRi is defined as reappearance of leukemic blasts in the peripheral blood or \geq 5% blasts in the bone marrow not attributable to any other cause (eg, bone marrow regeneration after consolidation therapy). In the setting of recent treatment, if there are no circulating blasts and the bone marrow contains 5% to 20% blasts, a repeat bone marrow performed at least a week later is necessary to distinguish relapse from regeneration.

Source: Cheson BD, Bennett JM, Kopecky KJ, et al. Revised Recommendations of the International Working Group for Diagnosis, Standardization of Response Criteria, Treatment Outcomes, and Reporting Standards for Therapeutic Trials in Acute Myeloid Leukemia. *J Clin Oncol* 2003;21:4642-9.

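### Two RFS censoring statements, in Section 10.1 and in the Table 4-1 primary estimand, do not exempt deaths and so, as written, censor some deaths that the endpoint counts as events

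*Combined protocol and SAP*

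**What the plan says.** Section 10.4.2 gives this definition of RFS: "time from randomization to the date of documented relapse after CR or CRi per central review, or death from any cause, whichever occurs first". Appendix 6 also counts death: its RFS entry runs "until the date of AML relapse or death from any cause, whichever occurs first".

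The censoring rules stand in three places:

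- **Section 10.1** has two consecutive sentences. The first is limited to participants without an RFS event and censors them at last contact. The second reads "RFS will be censored at the date of randomization for participants who were randomized but had no response assessment" and carries no such limit.
- **Table 4-1, primary estimand**, censors "Participants without documented relapse at the time of study closure", together with participants who are withdrawn or start subsequent therapy. Death is not mentioned.
- **Section 10.4.2** limits its main censoring rule to participants who are alive without relapse. It adds those "who were lost to follow-up without documented relapse, will be censored at the date of their last response assessment".

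Section 9.1.1 and Table 2-2 place the first scheduled post-baseline response assessment at Cycle 3. Section 9.1.1 also requires one at the Treatment Discontinuation Visit.

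**The concern.** An early death and a death in remission are both RFS events by definition. A programmer who followed the second sentence of Section 10.1, or the Table 4-1 row, would censor them. Deaths without relapse are where fatal toxicity would enter RFS, so censoring them flatters the arm that has more of them, and the censoring is informative.

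No hypothesis test is planned. The hazard ratio estimate is therefore itself the primary result, and it is to be set beside Study CC-486-AML-001. It will rest on very few events.

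**Working it through.** **Step 1: apply the rules to two records.**

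| Record | 10.4.2 definition | 10.1, no-assessment sentence | Table 4-1 as written |
|---|---|---|---|
| Dies Day 40, no post-baseline assessment | Event, Day 40 | Censored, Day 0 | Censored |
| Assessed at Cycle 3, dies in remission at month 5 | Event, month 5 | Does not apply | Censored |

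This takes a response assessment to mean a post-baseline one. Screening confirms CR/CRi, so if that counted, almost nobody would lack an assessment and the sentence would be empty.

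**Step 2: reproduce the plan's 87% (Section 10.2).** The inputs are 10 and 5 participants (10.2), medians of 9.5 and 4.8 months, and analysis when the last participant has 12 months' follow-up (10.1). RFS is taken as exponential, so HR = 4.8/9.5 = 0.505. The accrual period is not given; 0 to 24 months, uniform, is assumed.

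- Formula: P(estimated HR < 1) = Φ(√(d × 2/3 × 1/3) × |ln 0.505|), where d is the number of events.
- With d = 12: √2.667 × 0.683 = 1.115, and Φ(1.115) = 86.8%.
- Expected events run from 9.95 (no accrual spread) through 11.8 (12 months) and 12.4 (18 months) to 12.8 (24 months). The formula then gives 84.5% to 87.5%, and simulation of 200,000 trials gives 85.8% to 88.3%.

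The 87% reproduces when deaths count as events.

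**Step 3: RFS events before Cycle 3 Day 1.** Two 28-day cycles are 56 days, or 1.84 months.

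- Placebo: 1 − exp(−ln 2 × 1.84/4.8) = 0.233; × 5 = 1.17 events.
- CC-486: 1 − exp(−ln 2 × 1.84/9.5) = 0.126; × 10 = 1.26 events.
- Total: 2.42 events.

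**Step 4: how many the Section 10.1 rule loses.** Let q be the share of RFS events that are deaths without relapse, assumed equal in both arms and constant over time. Expected loss is 2.42q. The chance of at least one is 1 − (1 − 0.233q)^5 × (1 − 0.126q)^10.

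| q (assumed) | Expected deaths censored at Day 0 | Chance of at least one |
|---|---|---|
| 5% | 0.12 | 11% |
| 10% | 0.24 | 22% |
| 20% | 0.48 | 39% |
| 30% | 0.73 | 53% |

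These figures assume that no such participant had an earlier discontinuation-visit assessment, so they lean high.

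**Step 5: effect on the 87%.** In simulation with 12 months' accrual, the probability goes from 87.5% to between 87.4% (q = 5%) and 86.7% (q = 30%) under the Section 10.1 rule alone. If Table 4-1 were also applied as written, so that every death without relapse was censored, 0.6 to 3.5 of 11.8 events would be lost and the probability would be 86.8% to 82.3%.

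**Step 6: effect of one death on the estimate.** With 18 months' accrual, 7.68 CC-486 and 4.69 placebo events are expected. The hazard ratio is roughly a ratio of events per unit of follow-up, and follow-up changes little.

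- One CC-486 death censored: 6.68/7.68 = 0.87.
- One placebo death censored: 4.69/3.69 = 1.27.

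Cox fits to 4,000 simulated trials gave 0.87 and 1.26.

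**The case against.** The strongest reply is that nobody would program it this way. The second sentence of Section 10.1 can be read as a special case of the first, which is confined to participants without an event. Section 10.4.2 is the operational definition, and its main rule covers only participants who are alive. Section 10.4 leaves detail to a SAP finalized before database lock. This makes the intent fairly clear. It does not settle the text: the two Section 10.1 sentences give different censoring dates, so the second reads naturally as a separate rule, and Section 10.4.1 points to Table 4-1 for the estimands.

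The size can also be challenged, fairly. The share of deaths without relapse and the accrual period are assumed. With 12 events the standard error of the log hazard ratio is about 1/√(12 × 2/9) = 0.61, so a factor of 0.87 (0.14 on the log scale) is about a quarter of one standard error. No decision rule depends on it.

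A reader might infer three stronger points, which the documents do not support:

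- **That Section 10.4.2 censors known deaths among those lost to follow-up.** Section 8.3 treats the two cases separately. It says "If it is determined that the participant has died, the site will use permissible local methods to obtain date and cause of death", and uses the last known alive date only for participants who remain lost after all attempts. Section 10.4.2 also plans sensitivity analyses that count losses to follow-up as events, in both arms and then in the CC-486 arm only.
- **That the OS analysis discards known deaths**, because "Participants who dropout or are alive at study termination will have their OS times censored at the time of last contact". Section 10.4.3 defines OS as time to death from any cause and uses the date of death. Nowhere does it set a known date aside.
- **That Table 4-1 turns RFS into time to relapse.** The table lists death as an intercurrent event for time to relapse but not for RFS, which suggests that death was meant to belong to the RFS endpoint.

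**Conclusion.** The point holds for two statements: the no-assessment sentence in Section 10.1 and the study-closure clause in Table 4-1. Each, as written, conflicts with the event definition in Section 10.4.2 and Appendix 6. The conflict is probably unintended, but the text does not resolve it.

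The effect on the planning figure is negligible under the Section 10.1 rule alone. The effect on the primary estimate is modest but visible if such a death occurs, because one event is about 8% to 10% of the information (1/13 to 1/10). Its direction depends on the arm in which the death falls. These sizes rest on exponential RFS at the Section 10.1 medians, accrual of up to 24 months and deaths without relapse at 5% to 30% of events; the last two are not in the documents.

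**What to change.** Two wording changes, made before unblinding:

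1. **Section 10.1**, replace the no-assessment sentence with: *Participants with no RFS event (neither relapse nor death) and no post-randomization response assessment are censored at randomization; a death without a response assessment is an RFS event at the date of death.*
2. **Table 4-1, primary estimand**: insert *alive* after the first word of the study-closure clause, so that it covers only living participants without relapse.

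Optionally, state in Sections 10.4.2 and 10.4.3 that a death whose date is obtained counts as an event. That is a clarification only.

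The cost is editorial, since death dates are already collected. The estimates may become slightly less favourable to CC-486 if such deaths occur mainly in that arm.
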